As described in the *Estimation approach* subsection above, we will include covariates for the identified demographic characteristics and a baseline measure of the outcome of interest in each our benchmark models to increase the precision of our estimates and account for any small baseline differences between the treatment

and control groups.

iii. Additional covariates

We do not intend to include any further covariates beyond those specified in the *Estimation approach* subsection above.

Table 4. Covariates included in impact analyses

Covariate	Description of the covariate
Baseline primary outcome measures	
Frequency of vaginal sex without condoms in the past 30 days	
The risk outcome is operationalized as the number of times in the past 30 days a person reports having vaginal sex without using a condom.

	
The measure is calculated from the following item on the Participant Questionnaire:
 
 • In the past 30 days, how many times have you had vaginal sex without using a condom? 
The resulting variable is continuous with values that range from 0 to k, where 0 indicates that a person has not engaged in vaginal sex without a condom in the past 30 days, and k indicates the number of times the person has engaged in vaginal sex without a condom (risk behavior) in the past 30 days.
 
Note: All respondents who have baseline data and have provided a response to either this question or have indicated they have not had vaginal sex in the past 30 days will be included in the construction of this measure. Persons who indicate that they have not had vaginal sex in the past 30 days are coded as having vaginal sex without a condom zero times.

Current use of effective non-barrier contraception	
The protective outcome is operationalized as a dichotomous variable indicating whether a person reports currently using effective non-barrier contraception or not.

	
The measure is calculated from the following item on the Participant Questionnaire:
 
 • Please indicate which method of prescription birth control you currently using: 
 ○ Oral contraceptives (for example, the pill) ○ The patch (for example, Ortho Evra) ○ The shot/injection (for example, Depo-Provera) ○ The ring (for example, NuvaRing) ○ The implant (for example, Implanon or Nexplanon) ○ IUD (for example, ParaGard, Skyla, Mirena, Kyleena, Liletta) ○ None of the above 
A person who selects Oral contraceptives, patch, shot/injection, ring, implant, or IUD is given a value of 1 for the measure. A person who selects None is given a value of 0 for the measure.

	
The resulting variable is dichotomous with values 0 or 1, where 0 indicates a person who does not currently use effective non-barrier contraception and 1 indicates a person who does currently use effective non-barrier contraception.
 
Note: All respondents who have baseline data and have provided a response to this question will be included in the construction of this measure.

Number of sexual partners in the past 3 months	
The risk outcome is operationalized as the number of sexual partners in the past three months.

	
The measure is calculated from the following item on the Participant Questionnaire:
 
 • How many sexual partners have you had in the past 3 months? 
The resulting variable is continuous with values that range from 0 to k, where 0 indicates that a person has had no sexual partners in the past three months, and k indicates the number of sexual partners in the past three months.
 
Note: All respondents who have baseline data and have provided a response to this question will be included in the construction of this measure.

Individual-level covariates

Age	
The variable is measured as the respondent's self-reported age in years at screening.
 
The measure is constructed from the following item on the Eligibility Screening Form:
 
• Date of birth 
The variable is calculated by subtracting the reported date of birth given from the date when the screening was completed.
 
The resulting variable is continuous with values ranging from 16 to 21.

Gender	
The measure is operationalized a dummy variable, where 0 = identify otherwise; 1 = identify as female.
 
The measure is taken from the following item on the baseline Participant Questionnaire:
 
• What is your gender?
 Female Male Transgender female Transgender male Non-binary/genderqueer Unsure/questioning I do not identify as any of these (Would you like to indicate how you identify yourself? _____)
	
Variable will be coded as 1 if participant self-identified as female; if female is not selected, the response will be coded as 0.

Race	
The measure is operationalized as a dummy variable, where 0 = identify as another race and/or ethnicity; 1 = identify only as white.
 
The measure is taken from the following item on the baseline Participant Questionnaire:
 
• What is your race/ethnicity? (Participants can select more than one response)
 American Indian or Alaska Native Asian Black or African American Hispanic or Latino/a Native Hawaiian or other Pacific Islander White Some other race (specify)_____
	
Variable will be coded as 1 if participant self-identified as white only; if another race and/or ethnicity is selected or the respondent identifies as multiracial, the response will be coded as 0.

Hispanic /Latino/a	
The measure is operationalized as a dummy variable, where 0 = identify as another ethnicity/do not identify ethnicity; 1 = identify as Hispanic or Latino/a.
 
The measure is taken from the following item on the baseline Participant Questionnaire:
 
• What is your race/ethnicity? (Participants can select more than one response)
 American Indian or Alaska Native Asian Black or African American Hispanic or Latino/a Native Hawaiian or other Pacific Islander White

- Some other race (specify)

Variable will be coded as 1 if participant self-identified as *Hispanic or Latino/a*, regardless as to whether other races/ethnicities are specified; if Hispanic/Latino/a origin is not selected, the response will be coded as 0.

Blocking covariates

Study coordinat by State blocks	
A set of $n-1$ dummy variables, where n refers to the full set of study coordinator by state blocks within which participants are randomly assigned to the treatment or control condition. Participants are enrolled within one of 255 possible blocks defined by (1) the research coordinator who enrolled the participant into the study and (2) the state (or District of Columbia) where the participant indicated they would be most likely to seek reproductive health care. To clarify, each of the 5 research coordinators assign participants within one of their own 51 separate (state-and DC-based) random allocation lists, for a total potential 255 random allocation blocks.
 
Data for the measure are obtained from the Enrollment Log database (coordinator) and the Eligibility Screening Form (state).
 
Each dummy will be coded as 1 if the individual was jointly enrolled by a particular study coordinator and indicated they would be most likely to seek reproductive health care in a particular state, and 0 if otherwise. Dummy variables will be grand mean-centered so that the intercept will then reflect the unweighted mean study coordinator*state effect.

---------------------------------	---

f. Analytic approach for secondary research questions

For the secondary research questions listed under the subsection *Analysis of secondary outcomes in full sample using ITT approach* in the *Impact Study Research Questions* section, we will use the same analytic approach as described above under the *Benchmark analytic approach for primary research questions* subsection. For the secondary research questions listed under the subsection *Analysis of primary and secondary outcomes in subgroups using ITT approach*, models will also include a measure for the subgroup of interest and an interaction term for the subgroup and treatment to assess differences in subgroup impacts. For the secondary research questions listed under the subsection *CACE analysis of primary and secondary outcomes*, we will use CACE analysis. For this, we will assess the effect of MARSSI when individuals participate in (comply with) the program using two analytic methods derived from the principal stratification framework that estimate impact conditioned on endogenous (post-randomization) compliance: principal score weighting and two-stage least squares regression.³⁸ We will use the CACE methods described below when assessing these questions in both the full study sample and specified subgroups.

i. Principal score method

The first method we will use to estimate the CACE is a balancing procedure, based on propensity score methods, which can be used in settings where principal stratum membership (compliance) is observable under one treatment condition. The use of propensity scores is a common technique to balance treatment and comparison groups in nonexperimental studies; however,

³⁸ Frangakis, C. E., & Rubin, D. B. (2002). Principal stratification in causal inference. *Biometrics*, 58(1), 21–29. <https://doi.org/10.1111/j.0006-341x.2002.00021.x>

propensity score methods have also been used to address noncompliance in RCTs as well.³⁹

Within the context of a randomized trial using a 1:1 assignment ratio, there is an expectation that principal stratum membership should be equally allocated to the treatment and control groups. In other words, if there are compliers in the treatment group, we would expect there exists a similar group of individuals in the control group who would have complied if the program had been offered to them. Whereas the conventional use of propensity scores aims to model treatment group membership (where treatment group membership is the same as intervention receipt), the aim here is to use propensity scores to model treatment receipt (compliance) in the treatment group and subsequently predict probability of principal stratum membership among members of the control group.

In accordance with Hill et al. (2002), to distinguish this latter prediction step for the control group, we refer to their probability of principal stratum membership as the principal score.⁴⁰ The core assumption in propensity score methods is that of conditional ignorable treatment assignment, or the assertion that treatment assignment is independent of the potential outcomes, given a set of observed covariates (Rosenbaum & Rubin, 1983). When we use a probability score to balance treatment and control groups to estimate CACE in an RCT, this assumption now applies to principal stratum membership (compliance). In other words, principal stratum membership is independent of the potential outcomes given the observed set of covariates (Jo & Stuart, 2009).

We will follow the steps outlined in Stuart & Jo (2015) to estimate the CACE using principal score weights. Briefly, these will include: 1) using the same baseline covariates used in the benchmark analysis to predict compliance among the treatment group; 2) predicting the probability of compliance (principal score) among members of the control group; 3) creating analytic weights reflecting the probability of compliance; and 4) estimating CACE by fitting the outcome model using the principal score weights. Consistent with the ITT analysis, we will use an appropriate regression model (OLS for continuous/scale measures, logit for dichotomous, count for frequency) for each outcome. We will include the following covariates in each model: age, gender, race, ethnicity, randomization blocks, and the baseline measure of the outcome.

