BOSTON CHILDREN'S HOSPITAL

**EVALUATION OF THE MOMENTARY AFFECT REGULATION SAFER
SEX INTERVENTION**

OFFICE OF POPULATION AFFAIRS TEEN PREGNANCY PREVENTION PROGRAM

STATISTICAL ANALYSIS PLAN

NCT04798248

OCTOBER 2023

Submitted by:
The Policy & Research Group
www.policyandresearch.com

[name]
[name]

[name]
[name]

INTRODUCTION

OVERVIEW

In January 2023, The Policy & Research Group (PRG) submitted its Analysis Plan for the evaluation of the Momentary Affect Regulation Safer Sex Intervention (MARSSI) to Mathematica. In May 2023, Mathematica provided feedback to PRG on the plan.

In an effort to provide detail to other reviewers of this Analysis Plan (who may have similar questions), we include brief responses to key questions raised by Mathematica to offer further clarity on decisions made and how we intend to proceed with our analysis.

Reporting plan. In light of the number of research questions specified below, we want to be clear on how we intend to report findings from this evaluation. Our first priority will be to report results relevant to the three primary research questions using our benchmark analytic approach. This may include additional analyses, as needed, to clarify any analytical complications that invariably arise in the analysis of the impacts of complex social programs. We have noted some potential complexities in this Analysis Plan. Although it is not a requirement for an RCT with low attrition, we will include baseline equivalence statistics for each of the analytic samples used to produce findings for the three primary research questions. We may opt to include findings from secondary and exploratory research questions if we find that they elucidate or supplement the primary research findings.

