depressive symptoms score; 2) age; 3) race; 4) ethnicity; 5) gender; 6) Medicaid eligibility (proxy measure of healthcare access); 7) educational level; 8) recent receipt of sexual and reproductive health (SRH) information; 9) recent receipt of health services (mental health, SRH, and/or primary health care); 10) non-barrier contraceptive use; 11) main reason for using non-barrier contraception; 12) relationship status; 13) pregnancy intentions; and 14) feelings toward pregnancy.

CACE analysis of primary and secondary outcomes

What are the post-program, short-term, and long-term impacts of threshold participation in MARSSI on primary and secondary outcomes for a subgroup of participants assigned to treatment relative to a similar group of assigned to control?

2. Impact Study Design

This section provides a brief description of the study design and the process for creating intervention and comparison groups.

The BEhavior And Mindfulness Health (BEAM) study is an individual randomized controlled trial in which evaluators randomly assign eligible, consenting participants to intervention or comparison conditions at a one-to-one ratio. Random assignment occurs after participants' consent and before the provision of any programming or collection of baseline data.

Following submission of the baseline questionnaire, participants are implicitly informed of assignment through the discussion of next steps. Participants are enrolled on a rolling basis and randomized by the state where they would most likely seek reproductive health care and by the research coordinator who is enrolling them.⁴ See the *Random assignment process* section below for further details.

The treatment condition, MARSSI, is a motivational interviewing-based intervention designed specifically for adolescent and young adult (AYA) biologic females with depressive symptoms and sexual risk behavior. It aims to enhance motivation to change risky behaviors, provide skills to address depression's effects on behavior, and prompt and reinforce health-related affect regulation, cognitive behavioral skill use, and behavior change in daily life. MARSSI has three components: 1) a manualized counseling session with a sexual/reproductive health (SRH) counselor; 2) a mobile health application (mHealth app); and 3) a booster counseling session with the SRH counselor.

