To be eligible for enrollment, individuals must meet all of the following criteria: 1) biologically able to become pregnant; 2) 16-21 years of age;⁵ 3) fluent in English; 4) own a smartphone; 5) have the technical capacity to participate; 6) not currently pregnant; 7) not trying to become pregnant; 8) not have given birth during the six months preceding eligibility screening; 9) not be married or engaged to be married at the time of eligibility screening; 10) report having penile- vaginal sex in the past 3 months; 11) report having penile-vaginal sex at least once a week, on average; 12) score at least 8 on the PHQ-8 depression screening tool;⁶ 13) self-report visiting a reproductive health provider in the past two years;⁷ 14) report having done at least one of the following during the 3 months preceding eligibility screening: a) not used a condom every time they had sexual intercourse; b) used condoms, a diaphragm, cervical cap, spermicide, sponge, fertility awareness, or withdrawal as a primary form of birth control; c) had sexual intercourse with more than one person; d) had sexual intercourse within two hours after using drugs or alcohol; or e) been treated for a sexually transmitted infection/disease; 15) consent to participate in the study; and 16) not identified as fraudulent.⁸

The intent-to-treat sample (ITT) is comprised of eligible individuals who are enrolled into the study during the enrollment period (June 2021 to April 2023).

a. Random assignment process

- i. **Unit of randomization:** Random assignment occurs at the individual participant level.
- ii. **Random assignment procedure:** The Policy & Research Group (PRG) is responsible for all aspects of random assignment. Random assignment blocks of varying sizes assign participants to treatment or control condition at an equal (i.e., 1:1) assignment ratio. PRG produced this allocation list with an existing algorithm available in Stata (random allocation command, *ralloc*) and did so separately for each of the potential 255 study coordinator-state combinations.⁹ The allocation lists were produced by a PRG senior research analyst and stored on a secure server.

Electronic random assignment is conducted just prior to the administration of the online baseline questionnaire and is carried out by the study coordinators. Study coordinators were each given a sequential list of unique study IDs for every U.S. state. They assign a number (based on the state where the individual would seek

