reproductive health care) to each eligible and consented individual who is able to take the questionnaire through an online data collection platform. An individual is considered enrolled in the study and part of the ITT sample when they have been given a study ID number and completed the baseline questionnaire. Random assignment occurs when the unique study ID number is entered into a field in a web-based *Randomization Generator*. It is at this point that the ID number is associated with an assignment condition (treatment or control) in the random allocation sequence. At each baseline administration (after eligibility is confirmed), the study coordinator types in the ID number that was next on the list (going in ascending numerical order) into the study ID field of the *Randomization Generator*; the application then provides a message to the study coordinator that indicates the condition associated with that ID. While the participant completes the baseline questionnaire, the study coordinator records the participant's ID number and allocation into the study's electronic *Consent and Enrollment Form*.

Study participants are not explicitly informed of which condition (treatment or control) they are assigned; however, following their submission of the baseline questionnaire, a study coordinator implicitly informs the participant of assignment through the discussion of next steps (e.g., treatment participants are provided with the MARSSI main counseling session, control participants are provided with information for how they can listen to the podcast episode and are informed that they will be contacted in a month to complete the first follow-up questionnaire, to be administered one month post-baseline). With regards to messaging, the treatment and control interventions are never discussed as such; instead, study coordinators are trained to acknowledge that participants are randomly assigned to a particular intervention: a health program involving one-on-one video sessions with the study coordinator; or a health program that involves listening to a 20- minute podcast episode.

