In addition to carrying out the random assignment, PP-based study coordinators are responsible for monitoring the assignment process and ensuring fidelity to assignment is maintained. Every two weeks throughout the enrollment period, a PRG senior research analyst reviews participant IDs and assignment allocations recorded by study coordinators in the *Consent and Enrollment Form* database to ensure that they are both consistent with those in the original assignment list, and that participant IDs are assigned in sequential order as intended.

- iii. **Probability of assignment to treatment group:** The probability of assignment to the treatment group is intended to be equal to the probability of assignment to the control condition; that is, p (assignment to treatment) =.5.
- iv. **Potential for crossover/contamination:** To mitigate potential for both crossover¹⁰ and contamination¹¹, PRG study coordinators are trained in detailed study procedures;

¹⁰ PRG monitors crossover through routine data monitoring. Every two weeks, a senior research analyst checks to ensure that individuals assigned to the treatment condition are offered the MARSSI intervention, and that those assigned to the control condition are offered the podcast episode.

¹¹ In addition to crossover, it is possible that contamination may occur through interaction among participants. While it is possible

expectations regarding randomization are clear before implementation. Study coordinators commit to ensuring that participants randomly assigned to treatment participate in MARSSI and receive the intervention to fidelity, and participants randomly assigned to control receive information about how to access the podcast episode and do not receive any MARSSI content. Despite these efforts, there still remains the possibility that MARSSI participants may not receive some or all of the intervention program components, and control participants may receive some MARSSI content if study procedures are not followed by study coordinators or if SRH similar to MARSSI content is inadvertently delivered to a control participant.

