¹² Note: For the purposes of this study, delivery as intended requires that participants complete all MARSSI program components within six weeks of being enrolled into the study.

¹³ Session observation entails trained MARSSI observers watching recordings of the counselors delivering sessions to participants (virtually). Counselors are asked to record a certain number of each type of session per month, with the goal of recording and observing a minimum of 10% of all main counseling sessions and booster sessions delivered during the study period. Each recording is first viewed by two observers and then data are reconciled so that there is one final Observation Form associated with each video recording. Observers complete Observer Forms within one month after each recording.

Research question	Measure	Operationalization	Data sources
	counseling session during designated two-week window		
Dosage			
How much programming was received by participants?	Percent of participants who completed the main counseling session	Number of treatment participants who are indicated as having received the main counseling session divided by the total number of treatment participants enrolled in the study	Counselors complete an electronic Consent & Enrollment Session Form in which they indicate if they delivered the main counseling session and an electronic One-Month Follow-Up Data Collection Form in which they indicate if they delivered the booster session.
	Percent of participants who completed at least 14 days of app use	Number of treatment participants who have an indicator of at least 14 days of submitting at least one response in the app divided by the total number of treatment participants enrolled in the study ¹⁴	
	Percent of participants who completed the booster session	Number of treatment participants who are indicated as having received the booster session divided by the total number of treatment participants enrolled in the study	

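### Section 2 makes baseline completion, which follows randomization, a condition of belonging to the ITT sample; Section 4 works from everyone randomized

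*SAP*

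**What the plan says.** **Order of events.** Section 2 (Impact Study Design) places random assignment after consent and "before the provision of any programming or collection of baseline data". Section 2.a.ii (Random assignment procedure) agrees: "Electronic random assignment is conducted just prior to the administration of the online baseline questionnaire". Assignment happens when the coordinator enters the study ID in the Randomization Generator, and "the application then provides a message to the study coordinator that indicates the condition associated with that ID". The participant learns the arm, implicitly, only after submitting the questionnaire.

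**ITT in Section 2.** The design text says: "The intent-to-treat sample (ITT) is comprised of eligible individuals who are enrolled into the study during the enrollment period". Section 2.a.ii then says what being enrolled means: a person is enrolled and "part of the ITT sample when they have been given a study ID number and completed the baseline questionnaire".

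**The sample in Section 4.**
- 4.c (Analytic sample(s)) makes randomization the moment a person becomes a participant. It takes as the primary sample all those randomized who supply the outcome data, and imputes missing baseline data.
- 4.e (Benchmark analytic approach) describes the ITT framework as keeping all those randomized apart from those lost to attrition.
- 4.a.iii.b and step d of 4.a.iv both start from the randomized sample.
- 4.e.i (Estimation approach) uses the full randomized sample and the ITT sample as the same reference set within one argument about single-participant blocks.

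**The concern.** An ITT sample should be fixed by randomization. Under the Section 2 rule, someone who was randomized but did not finish the questionnaire was never in the ITT sample, so an ITT count would omit that person, and so would an attrition rate based on it. During that interval the coordinator, who is also the counselor for the treatment arm, already knows the allocation. Nothing suggests misuse, but the interval is not blind on the staff side.

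The SAP leans on attrition. Section 4.a.iv rests the causal claim on randomization at the point of offer. Footnote 35 in 4.e.i assumes low overall and differential attrition for an unbiased estimate. The Reporting plan in the Introduction also invokes it: "Although it is not a requirement for an RCT with low attrition, we will include baseline equivalence statistics". The benchmark equivalence check cannot reveal this loss, because Section 4.d restricts it to people with both baseline and outcome data.

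A smaller point concerns the dosage rows of Table 1, where percentages are "divided by the total number of treatment participants enrolled in the study". Section 2.a.ii ties enrollment to a completed baseline. Section 4.c mentions enrolling alongside randomization and is silent on baseline. Table 1 does not say which meaning it uses.

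**Working it through.** **Step 1: who falls between the definitions.** Take a person who consented, whose ID was entered in the Randomization Generator, and who did not complete the baseline questionnaire.

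| Place in the SAP | Status of this person |
|---|---|
| 2 and 2.a.ii | Not enrolled, not in the ITT sample |
| 4.c | A participant; in the primary sample if outcome data exist |
| 4.a.iii.b and 4.a.iv step e | Missing baseline handled by dummy variable adjustment, not a ground for exclusion |
| 4.a.iv step d | In the randomized sample; counted as attrition if outcome data are missing |
| 4.e | Included unless lost to attrition |

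The definitions give the same set only if there are no such people. The SAP gives no number for them in either arm, so there is no plan figure to reproduce.

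**Step 2: bound on overall attrition.** Let
- b = share of those randomized who did not complete baseline (assumption);
- a = share of baseline completers later lost (left free);
- r = share of baseline non-completers who still give outcome data (left free).

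Attrition counted from completers is a. Counted from randomization it is

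A = 1 − [(1 − b)(1 − a) + b·r] = a + b(1 − a − r),

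so A − a = b(1 − a − r). Since a and r each lie between 0 and 1, the bracket lies between −1 and 1, and |A − a| ≤ b.

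| b (assumed) | Range of A − a over all a and r |
|---|---|
| 0 | 0 |
| 1% | −1 to +1 percentage point |
| 5% | −5 to +5 percentage points |

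**Step 3: bound on differential attrition.** If non-completers give no outcome data (r = 0), each arm's gap is b(1 − a), between 0 and b. The shift in the treatment-minus-control difference is

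b_T(1 − a_T) − b_C(1 − a_C),

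which lies between −b_C and b_T. Its size is therefore at most the larger of b_T and b_C.

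**Step 4: effect on the primary estimate.** Where the 4.c sample is used, the estimate does not change. With r = 0 the analysed people are the same under either definition, because non-completers have no outcome to analyse. Only the denominator moves.

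**The case against.** The strongest reply is that no planned analysis changes. Section 4 governs the primary sample and sets no baseline condition. Step d already starts from the randomized sample, and step b already reports missingness for each arm. No passage says attrition will be taken from the Section 2 definition. The interval is also short: IDs go to people who are able to take the questionnaire, and participants cannot decline baseline because of their arm, since they do not yet know it. The number lost may be zero, and the 1% and 5% values have no anchor in the SAP.

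Much of this stands. It limits the practical consequence, and it shows that randomization is the natural reading of step d. The Reporting plan is weak support too, since equivalence statistics will be reported whatever the attrition. The Table 1 point is minor: its percentages are descriptive, and Section 4.c does not define enrollment in a clearly different sense.

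The reply does not remove the conflict. Section 2 is where the SAP says who belongs to the ITT sample, and what it says is wrong for a trial that randomizes before baseline. Step d promises attrition statistics without naming the denominator of the rate, so two readers could report different figures. That Section 4 is sound is a reason to bring Section 2 into line with it.

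**Conclusion.** The concern holds. Section 2 conditions ITT membership on a post-randomization event and contradicts Section 4. The textual conflict is certain; its practical size is not known from the SAP. Overall attrition could be misstated by at most the share randomized without a completed baseline, and differential attrition by at most the larger arm's share if those people give no outcome data. Both are zero if nobody was lost in that interval. The primary impact estimate is unaffected as long as the Section 4.c sample is used. This should be corrected because attrition supports the SAP's claim of an unbiased estimate, but it is a fault of definition and reporting and not of the primary model.

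**What to change.** 1. In Section 2 and Section 2.a.ii, define the ITT sample as everyone randomized, meaning everyone whose ID was entered in the Randomization Generator.
2. In Section 4.a.iv step d, state that this sample is the denominator for overall and differential attrition.
3. Report by arm the number randomized who did not complete the baseline questionnaire.
4. In Table 1, state whether the enrolled denominator means randomized.

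Section 4.c needs no change.

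The cost is SAP wording and one count by arm. Allocations are recorded in the Consent and Enrollment Form, a two-weekly review checks that "participant IDs are assigned in sequential order as intended", and the questionnaire in Appendix A asks for the ID, so IDs used can be matched to questionnaires submitted. The SAP does not say that the Randomization Generator keeps its own log, so the count may be incomplete and should be reported with that caveat. Reported attrition may come out slightly less favorable.
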